17.2. SECONDARY IMMUNOGENICITY

17.2.1. SECONDARY IMMUNOGENICITY VARIABLE & DERIVATION

The secondary objective is to evaluate the immune response of VNS vaccine (formulated with different potencies) and VV vaccine in terms of seroresponse rate* at Day 43 and will be based on the PPS and ES.

* Seroresponse rate is defined as the percentage of participants for whom the post-dose anti-VZV gE antibody concentration (Day 43) is ≥ 300 mIU/mL.

17.2.2. MISSING DATA METHODS FOR SECONDARY IMMUNOGENICITY VARIABLE

Missing data will not be replaced. Please refer to section 8.3 for more details

17.2.3. ANALYSIS OF SECONDARY IMMUNOGENICITY VARIABLE

The percentage of participants with a seroresponse will be summarized by intervention groups and corresponding 2-sided 95% exact CI will be reported based on Clopper and Pearson method.

Document: \\quintiles.net\\enterprise\\Apps\\sasdata\\SASb\\SAS\\GlaxoSmithKline\\VNS\\217212\\VNS 20-006\\Biostatistics\\Documentation\\SAP\\GSK_217212\\VNS 20-006\\ZZA47662_SAP_Final_v7_24Jun2024.docx

Author: PPD Version Number: 7.0
Version Date: 24Jun2024

Template No.: CS_TP_BS016 Revision 6

Reference: CS_WI_BS005

Effective Date: 02Dec2019

The analysis will also be done split by country.

The number and percentage of participants with a seroresponse at Day 43 and 2-sided 95% CI on group difference in the seroresponse rate (VV pooled group-VNS group [different potencies – Low, Med, High]) will be computed based on Miettinen and Nurminen method [Miettinen, 1985].

For interim analyses, seroresponse will be analyzed using a logistic regression with VNS dose level used as a covariate. The dose effect will be constrained to be positive.

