**Objectives, Endpoints, and Estimands:** The study will evaluate the immune response of the investigational VNS vaccine (formulated at 3 different potencies) and the VV vaccine in terms of geometric mean concentration (GMC) and in terms of seroresponse rate (percentage of participants for whom the post-dose anti-glycoprotein E [gE] antibody concentration is  $\geq 300$  mIU/mL) to gE. The study will also evaluate the safety and the reactogenicity (incidence of solicited adverse events [AEs], unsolicited AEs, and serious adverse events [SAEs]) following the administration of the VNS and VV vaccines.

**Overall Design:** This will be a phase II, observer-blind, randomized, multicenter controlled study with 5 parallel intervention groups of healthy children aged 12 to 15 months at the time of intervention. Participants will be randomized to receive a single dose of an investigational varicella vaccine (3 groups each receiving one of the 3 different vaccine potencies [a low, medium, and high potency of the VNS vaccine, respectively]) or a single dose of a comparator licensed varicella vaccine (2 groups each receiving one of the 2 different lots of the VV vaccine, which will be pooled for all analyses). All participants in the US will be co-administered with MMR, *Havrix*, and *Prevnar 13* vaccines. Participants recruited outside of the US will be co-administered with MMR, *Havrix*, and in some countries, with *Prevnar 13*. Outside the US,

*Prevnar 13* will only be administered in countries where pneumococcal conjugate vaccine is recommended at 12-15 months as per national immunization schedule. If *Prevnar 13* is to be administered, participants are required to have previously received the primary series of pneumococcal conjugate vaccine in their first year of life with last dose at least 60 days prior to study entry.

Randomization to one of the 5 groups will be performed in a 2:2:2:1:1 ratio prior to intervention. There will be 3 study visits, at Day 1 (intervention), Day 15 (virtual or in-person), and Day 43, as well as 1 safety call and 1 safety follow-up contact, at Day 2-3 and Day 181, respectively.

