#### **6.3.2 Randomization to Study Intervention**

The country and center will be used as minimization factors for randomization. Randomization of vaccines will be performed using Interactive Voice Response System (IVRS)/Interactive Web Response System (IWRS). The participants will receive a unique treatment number (refer to [Appendix 1](#) for the definition). Once a treatment number has been assigned, it cannot be re-assigned.

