## 9.0 STATISTICAL CONSIDERATIONS

### 9.1 Statistical Hypotheses

There are no statistical hypotheses in this study. All analyses are descriptive.

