### 9.4.2 Primary Endpoint Analyses

The primary analysis of immunogenicity endpoints will be based on the PPS.

The geometric mean concentrations (GMCs) will be summarized by group with their 95% CI derived considering log-transformed anti-gE antibody concentrations are normally distributed with unknown variance. The concentration below the assay cut-off will be assigned half the cut-off for the purpose of GMC computation.

The group GMC ratio with nominal 95% CI will also be provided. This will be obtained using an analysis of variance (ANOVA) model on log-transformed concentrations. The model based on the data from all groups will include group and country as a fixed effect.

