#### **9.4.3 Secondary Endpoints Analyses**

The analysis of secondary immunogenicity endpoints will be primarily based on the PPS.

Seroresponse rate is defined as the percentage of participants for whom the post-dose anti-gE antibody concentration (Day 43) is  $\geq 300$  mIU/mL.

The seroresponse rates will be summarized by group with their 95% exact CI based on Clopper-Pearson method [[Clopper and Pearson, 1934](#)].

The 2-sided 95% CI on group difference in seroresponse rate (pooled VV group minus each VNS group [Low, Med, High]) will be computed based on the method of Miettinen and Nurminen [[Miettinen and Nurminen, 1985](#)].

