2.0	28OCT2021	PPD [REDACTED]	
Update following protocol amendment 1 dated 8th October 2021, CBER feedback and to complete the analysis specification:
 
 • Update reference to protocol amendment 1 • New study visit at Day 15 and safety call at Day 2-3 • SRT to be monthly rather than frequently • Update prior medication definition to include all medications started before first dose of study treatment • Ensure consistency on missing data • Varicella-like rash now includes injection site varicella-like rash • Clarified solicited and unsolicited adverse events analysis • Include intensity grades for fever and updated grades for varicella-like rash
3.0	25NOV2021	PPD [REDACTED]	
Update following protocol amendment 2 dated 15th November 2021:
 
 • Include general rash (not varicella-like), drowsiness, irritability and loss of appetite as solicited events

Document: \\quintiles.net\enterprise\Apps\sasdata\SASb\SAS\GlaxoSmithKline\VNS\217212\VNS 20-006\Biostatistics\Documentation\SAP\ GSK_217212\VNS 20-006_ZZA47662_SAP_Final_v7_24Jun2024.docx

Author: PPD Version Number: 7.0
 Version Date: 24Jun2024

Template No.: CS_TP_BS016 Revision 6

Reference: CS_WI_BS005

Effective Date: 02Dec2019

4.0	09JUN2022	PPD	Include countries other than the US. Prevnar 13 not administered in all countries. Include new analysis split by country, duration of solicited events and ongoing solicited events post the solicited period.
5.0	27SEP2022	PPD	Update following the Spanish protocol amendment – adding a co-administered meningococcal vaccine visit at Day 15 for Spain. Update algorithm in appendix 2 to be consistent with section 15.
6.0	04MAR2024	PPD	Reverted update made for the Spanish protocol amendment in SAP version 5. Added derivation for age. Added country as fixed effect to all models. Updated the MedDRA version number and Preferred Terms for Drowsiness and Loss of appetite. Updated Preferred Terms for unsolicited adverse events that are synonymous with solicited adverse events. Added details for handling duplicate solicited adverse events. Explained handling of solicited events recorded beyond the end of the solicited periods. Added definition of immediate unsolicited AEs.
7.0	24JUN2024	PPD	Added Section 18.1.1.1 eCOA Compliance.

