7.5. STATISTICAL TESTS

The default significant level will be (5%); 2-sided confidence intervals (CIs) will be 95%, unless otherwise specified in the description of the analyses.

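### The seroresponse-rate difference has no country-stratified interval, although allocation is minimised on country and the GMC ratio is meant to be country-adjusted

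*SAP*

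**What the plan says.** **Allocation.** Protocol 6.3.2: "The country and center will be used as minimization factors for randomization".

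**Primary comparison.** For the GMC ratio, Protocol 9.4.2 states: "The model based on the data from all groups will include group and country as a fixed effect". SAP 8.1 agrees, and the version 6.0 entry in the SAP history reads "Added country as fixed effect to all models". SAP 17.1.3, however, names only intervention group in the same model.

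**Secondary comparison.** The pooled-VV-minus-VNS difference in seroresponse rate, one for each potency, "will be computed based on the method of Miettinen and Nurminen" in Protocol 9.4.3, and "will be computed based on Miettinen and Nurminen method" in SAP 17.2.3. Neither section names a stratum, a weight or a covariate.

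**Other seroresponse analyses.** SAP 17.2.3 repeats the seroresponse summary by country. SAP 8.1 adds, for the interim analysis, a logistic regression on VNS dose level with country as a fixed effect. SAP 17.2.3 repeats that model without naming country. SAP 5.3 makes clear that this interim analysis holds the final Day 43 immunogenicity data.

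**Status.** Protocol 9.1: "There are no statistical hypotheses in this study. All analyses are descriptive".

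**The concern.** The plan brings country into the allocation and into the GMC comparison. The seroresponse difference is a two-sample calculation and not a model, so a change that added country to all models did not reach it. The two comparisons with Varivax will be read side by side, yet they treat country differently and the plan gives no reason.

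Two things could follow. If seroresponse rates differ between countries and the groups are balanced by country, the unstratified interval carries between-country variation that stratification removes. If exclusions from the Per Protocol Set (PPS) leave the groups with different country mixes, the crude difference absorbs part of the gap between countries. Equal rates across countries cannot be presumed: Prevnar 13 use and the MMR brand vary by country (Protocol 1.1).

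**Working it through.** **Inputs from the documents.** Target enrolment is 800, allocated 2:2:2:1:1 with the two VV lots pooled, so 800 × 2/8 = 200 per analysed group. Protocol 9.2 allows 10% unevaluable: 200 × 0.9 = 180 in the PPS per group. Intervals are two-sided 95%.

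**Assumed.** Two countries of equal size, with the rates listed below and no true group difference. The documents give no number of countries, country shares or country-specific rates.

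**The plan's own figures.** No figure is given for a between-group difference. The nearest check is Protocol Table 10: the Clopper-Pearson interval for 162/180 reproduces as 84.66% to 93.96%. The other rows also reproduce, apart from one upper limit printed as 89.885%, which computes to 89.876% and has no bearing here.

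**1. Width when countries are balanced.** The stratified difference is d = Σ w_k(p_1k − p_2k), with w_k proportional to n_1k·n_2k/(n_1k + n_2k). Its interval inverts the Miettinen-Nurminen score statistic, with restricted maximum-likelihood rates and the N/(N−1) variance factor in each stratum. With 90 per country per group:

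| Country rates | Crude, ± points | Stratified, ± points | Crude wider by |
|---|---|---|---|
| 85% / 95% | 6.40 | 6.38 | 0.2% |
| 80% / 95% | 6.98 | 6.91 | 1.0% |
| 75% / 95% | 7.49 | 7.33 | 2.2% |
| 70% / 98% | 7.68 | 7.38 | 4.0% |

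**2. Random loss from the PPS.** Simulation of 4,000 trials per scenario, with 100 per country per group at entry and 10% independent loss:

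| Country rates | Crude and stratified estimates differ, in 95% of trials, by at most | Coverage, crude v stratified | Mean width, crude v stratified |
|---|---|---|---|
| 95% / 85% | 0.36 points | 95.8% v 95.5% | 12.72 v 12.68 points |
| 98% / 78% | 0.66 points | 96.5% v 95.4% | 13.70 v 13.49 points |

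**3. Unequal loss by country.** Shift in the crude difference = (difference in country share between groups) × (gap in rates between countries).

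- A 5-point difference in mix with rates of 80% and 95%: 0.05 × 15 = 0.75 points.
- A 10-point difference in mix: 0.10 × 15 = 1.5 points.

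**4. How large the mix difference can become.** Start from 100/100 in each group and lose 20 per group.

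- One group loses evenly (90/90). The other reaches a 45% share of one country only at 81/180, so 19 of its 20 losses must come from that country. That gives 5 points.
- A 10-point difference needs 81/99 against 99/81, that is, 19 of 20 losses from opposite countries in the two groups.
- The ceiling is 80/100 against 100/80: 100/180 − 80/180 = 11.1 points.

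**5. Example at the ceiling.** Rates are 95% and 85% in both groups. VV is split 100/80 and has 95 + 68 = 163 responders of 180. VNS is split 80/100 and has 76 + 85 = 161 of 180. The crude difference is 1.11 points [−5.26; 7.53]. The stratified difference is 0.00 [−6.42; 6.43].

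**The case against.** The strongest reply is that both intervals are valid descriptive summaries and little separates them. Minimisation limits country imbalance at entry, and observer-blinding makes strongly differential exclusion unlikely. Nothing in the trial is decided by the interval. Seroresponse is also reported on the Exposed Set, which gives a further check on PPS exclusions. Center is a minimisation factor too, so stratifying by country alone reflects only part of the allocation. All of this stands, and it limits how much weight the point can carry. Choosing country and not center is at least consistent with the plan's own GMC model, which omits center.

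Four stronger readings are tempting, and the documents do not support them:

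- **That country is ignored for seroresponse.** It is not, given the by-country split and the country term in the interim logistic regression. What is missing is narrower. The split gives separate, smaller-sample results. The regression models dose level with its effect constrained to be positive. Neither yields an adjusted rate difference for each potency.
- **That the unstratified interval overstates certainty.** With balanced countries it errs on the wide side.
- **That the gain in precision is larger.** The large-sample variance ratio, √[p(1−p)/Σ w_k p_k(1−p_k)] with p the overall rate, gives 1.4%, 2.7%, 4.2% and 8.2% for the four rate pairs. Those figures do not describe the Miettinen-Nurminen intervals, whose differences are about half as large or less.
- **That the GMC ratio is settled as country-adjusted.** Protocol 9.4.2 and SAP 8.1 say so, but the wording of SAP 17.1.3 does not.

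**Conclusion.** The point holds in a limited form. The plan provides no country-adjusted seroresponse difference for each VNS group, although country is a minimisation factor and the GMC ratio is meant to be adjusted for it.

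The consequence is small. Under balance the crude interval is 0.2% to 4.0% too wide over the rate pairs examined. Under random loss the two estimates agree to within about 0.4 to 0.7 points in 95% of trials, against an interval roughly 13 points wide. A shift of 0.75 points needs almost all of one group's losses to fall in one country, and a 10-point difference in mix is close to the arithmetic limit of 11.1. The gain lies mainly in consistency between the two endpoints and in protection against a chance or differential country imbalance.

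These sizes rest on two equal countries and assumed rates. The actual effect cannot be fixed from the documents, and it is nil if rates do not differ between countries.

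**What to change.** In SAP 17.2.3, and in Protocol 9.4.3 if it is next amended:

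- Compute each pooled-VV-minus-VNS difference and its 95% CI by the Miettinen-Nurminen method stratified by country.
- State the weights, for example n_1·n_2/(n_1 + n_2) within each country.
- Fix, before unblinding, a rule for merging countries too small to form a stratum.
- Show the crude interval beside the stratified one.

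Name country in SAP 17.1.3 and in the logistic regression of SAP 17.2.3 at the same time, so that they agree with SAP 8.1.

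The cost is a few lines of SAP text and a stratified form of the same method; no new data are needed. There are two small drawbacks. The stratified difference will not exactly equal the difference between the tabulated percentages, which a footnote can explain, and very small countries have to be merged.

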18. SAFETY OUTCOMES

All outputs for safety outcomes will be based on the ES.

There will be no statistical comparisons between the treatment groups for safety data.

Secondary Safety Endpoints:

- Solicited events
 - Percentage of participants reporting each solicited administration site event in terms of injection site redness, pain and swelling within 4 days (Day 1 to Day 4) post-dose of VNS vaccine or VV vaccine
 - Percentage of participants reporting each solicited systemic event in terms of fever, varicella-like rash (including injection site varicella-like rash) and general rash (not varicella-like) within 43 days (Day 1 to Day 43) post-dose of study interventions at Day 1
 - Percentage of participants reporting each solicited systemic event in terms of drowsiness, loss of appetite and irritability within 15 days (Day 1 to Day 15) post-dose of study interventions at Day 1
- Unsolicited adverse events
 - Percentage of participants reporting unsolicited AEs within 43 days (Day 1 to Day 43)

Document: \\quintiles.net\enterprise\Apps\sasdata\SASb\SAS\GlaxoSmithKline\VNS\217212(VNS 20-006)\Biostatistics\Documentation\SAP\ GSK_217212(VNS 20-006)_ZZA47662_SAP_Final_v7_24Jun2024.docx

Author: PPD Version Number: 7.0
Version Date: 24Jun2024

Template No.: CS_TP_BS016 Revision 6

Reference: CS_WI_BS005

Effective Date: 02Dec2019

43) post-dose of study interventions at Day 1

- Serious adverse events
 - Percentage of participants reporting SAEs post-dose of study interventions at Day 1 up to the end of study

18.1. ADVERSE EVENTS

AEs will be coded using MedDRA central coding dictionary, Version 26.1 or higher. Adverse events will be described using frequency and percentage.

AEs will be grouped by SOC and PT and summarized by intervention at time of onset of the AE. The summary tables will present the number and percentage of total participants and number of events, by SOC and by PT for each intervention group.

For the summaries of AEs, participants who experience the same AE (in terms of the MedDRA SOC and PT) more than once will only be counted once for that event in the number of participants but all occurrences of the same event will be counted in the number of events.

See APPENDIX 2 for handling of partial dates for AEs. In the case where it is not possible to define an AE as pre-treatment or treatment-emergent (TEAE) due to missing or partial dates, the AE will be classified by the worst case; i.e., TEAE. TEAE are defined as AEs which commence on or after the time of the vaccine administration through to the study end. All AE summaries will be restricted to TEAEs only.

Listings of all AEs and SAEs leading to discontinuation of study will be provided.

18.1.1. SOLICITED ADVERSE EVENTS

Solicited events are recorded in electronic diaries. Duplicate entries are defined as records with identical participant ID, category, object of the observation, date and time of collection, result or

Document: \\quintiles.net\enterprise\Apps\sasdata\SASb\SAS\GlaxoSmithKline\VNS\217212\VNS 20-006\Biostatistics\Documentation\SAP\ GSK_217212\VNS 20-006_ZZA47662_SAP_Final_v7_24Jun2024.docx

Author: PPD Version Number: 7.0
Version Date: 24Jun2024

Template No.: CS_TP_BS016 Revision 6 Reference: CS_WI_BS005

Effective Date: 02Dec2019

finding in original units and evaluator. In case of duplicate records, the first record will be kept for analysis. The first record is determined by sequence number assigned in the SDTM dataset.

In the event the electronic diary was started later than the day of vaccination, it remained open to record solicited events beyond the end of the solicited periods. Data beyond the solicited period will remain in the datasets but will not be used in the statistical analysis, since the solicited period is based on Study Day for the statistical analyses, see section 7.1.

For each study group and each solicited event, the incidence rates (frequencies and percentages) of vaccinated participants with solicited administration site events, systemic events (drowsiness, loss of appetite and irritability) and systemic events (fever, varicella-like rash (including injection site varicella-like rash) and general rash) collected within 4 days (Day 1 to Day 4), within 15 days (Day 1 to Day 15) and within 43 days (Day 1 to Day 43) respectively will be summarized (percentage of vaccinated participants with each of any, grade 2 or 3, related, grade 3 leading to medical attention). The completeness defined as the percentage of vaccinated participants who documented presence/absence of each event as well as the daily prevalence of each symptom among vaccinated participants who documented presence /absence of the event on that day will be provided. These will also be summarized for each country.

The duration of each solicited event, in days, will be summarized using descriptive statistics (n, mean, standard deviation, median and range) for each study group. The duration will be calculated from the first date that the symptom was reported up to the last date the symptom was reported ignoring any dates when the symptom was absent or was not recorded: Last date symptom recorded – first date symptom recorded + 1

The number of solicited events still ongoing at the end of the solicited period will be summarized by study group by maximum intensity (any, grade 2-3 and grade 3).

Solicited administration site events	Solicited systemic events
Pain at Injection Site	Fever

Document: \\quintiles.net\enterprise\Apps\lsasdata\SASb\SAS\GlaxoSmithKline\VNS\217212\VNS 20-006\Biostatistics\Documentation\SAP\ GSK_217212\VNS 20-006_ZZA47662_SAP_Final_v7_24Jun2024.docx

Author: PPD Version Number: 7.0

Version Date: 24Jun2024

Template No.: CS_TP_BS016 Revision 6

Reference: CS_WI_BS005

Effective Date: 02Dec2019

Solicited administration site events	Solicited systemic events
Redness at Injection Site	Varicella-like rash (including injection site varicella-like rash)
Swelling at Injection Site	General rash (not varicella-like) Drowsiness Loss of appetite Irritability

Intensity Scales for Solicited Events in Toddlers (12 to 15 Months of Age) will be assessed as follows:

Adverse Event	MedDRA Preferred Term	Intensity Grade	Parameter
Pain at Injection Site	Administration site pain (10058049)	0	None
		1	Mild: Minor reaction to touch
		2	Moderate: Cries/protests on touch
		3	Severe: Cries when limb is moved/spontaneously painful
Redness at Injection Site	Administration site erythema (10074796)	0	None
		1	> 0 - ≤ 5 mm
		2	> 5 - ≤ 20 mm
		3	> 20 mm
Swelling at Injection Site	Administration site swelling (10075107)	0	None
		1	> 0 - ≤ 5 mm
		2	> 5 - ≤ 20 mm

Document: \\quintiles.net\enterprise\Apps\asadata\SASb\SAS\GlaxoSmithKline\VNS\217212\VNS 20-006\Biostatistics\Documentation\SAP\ GSK_217212\VNS 20-006_ZZA47662_SAP_Final_v7_24Jun2024.docx

Author: PPD Version Number: 7.0
 Version Date: 24Jun2024

Template No.: CS_TP_BS016 Revision 6

Reference: CS_WI_BS005

Effective Date: 02Dec2019

Copyright © 2009, 2010, 2012, 2016, 2018, 2019 IQVIA. All rights reserved. The contents of this document are confidential and proprietary to IQVIA Holdings Inc. and its subsidiaries. Unauthorized use, disclosure or reproduction is strictly prohibited.

Adverse Event	MedDRA Preferred Term	Intensity Grade	Parameter
		3	> 20 mm
Fever*	Pyrexia (10037660)	0	<38.0°C (100.4°F)
		1	≥ 38.0°C (≥ 100.4°F) - ≤ 39.0°C (≥ 102.2°F)
		2	> 39.0°C (≥ 102.2°F) - ≤ 39.5°C (≥ 103.1°F)
		3	> 39.5°C (≥ 103.1°F)
Varicella-like rash (including injection site varicella-like rash)	Rash vesicular (10052566)	0	None
		1	1-25 lesions
		2	26-50 lesions
		3	≥51 lesions
General rash (not varicella-like)	General rash (10049201)	0	None
		1	Mild: Rash which is easily tolerated by the child, causing minimal discomfort and not interfering with everyday activities
		2	Moderate: Rash which is sufficiently discomforting to interfere with normal everyday activities
		3	Severe: Rash which prevents normal, everyday activities (in a young child, such an AE would, for example, prevent attendance at school/day care and would cause the parent(s)/LAR(s) to seek medical advice)
Drowsiness	Lowest level term: Drowsiness (10013649)	0	Behaviour as usual
		1	Mild: Drowsiness easily tolerated
		2	Moderate: Drowsiness that interferes with normal activity

Document: \\quintiles.net\enterprise\Apps\sasdata\SASb\SAS\GlaxoSmithKline\VNS\217212\VNS 20-006\Biostatistics\Documentation\SAP\ GSK_217212\VNS 20-006_ZZA47662_SAP_Final_v7_24Jun2024.docx

Author: PPD Version Number: 7.0
 Version Date: 24Jun2024

Template No.: CS_TP_BS016 Revision 6

Reference: CS_WI_BS005

Effective Date: 02Dec2019

Adverse Event	MedDRA Preferred Term	Intensity Grade	Parameter
	PT: Somnolence (10041349)	3	Severe: Drowsiness that prevents normal activity
Loss of appetite	Decreased appetite (10061428)	0	Appetite as usual
		1	Mild: Eating less than usual/ no effect on normal activity
		2	Moderate: Eating less than usual/ interferes with normal activity
		3	Severe: Not eating at all
Irritability	Irritability (10022998)	0	Behavior as usual
		1	Mild: Crying more than usual/no effect on normal activity
		2	Moderate: Crying more than usual/ interferes with normal activity
		3	Severe: Crying that cannot be comforted/ prevents normal activity

* Temperature will be analyzed in 0.5°C increments from $\geq 38.0^{\circ}\text{C}$ ($\geq 100.4^{\circ}\text{F}$)

The number and percentage of participants per study intervention reporting unsolicited adverse events with MedDRA preferred terms that are synonymous with solicited adverse events, and starting after the end of each solicited period, will be summarized by severity (mild, moderate or severe). If a participant experiences an event on more than one occasion, the maximum intensity will be reported. The following table shows the corresponding MedDRA preferred terms or higher level terms that will be selected from the unsolicited adverse events for this analysis.

Document: \\quintiles.net\enterprise\Apps\lsasdata\SASb\SAS\GlaxoSmithKline\VNS\217212\VNS 20-006\Biostatistics\Documentation\SAP\ GSK_217212\VNS 20-006)_ZZA47662_SAP_Final_v7_24Jun2024.docx

Author: PPD Version Number: 7.0
 Version Date: 24Jun2024

Template No.: CS_TP_BS016 Revision 6

Reference: CS_WI_BS005

Effective Date: 02Dec2019

Unsolicited adverse events that are synonymous with solicited adverse events

Solicited Adverse Event	MedDRA PT/HLT
Pain at injection site	Administration site pain (PT)
Redness at injection site	Administration site erythema (PT)
Swelling at injection site	Administration site swelling (PT)
Drowsiness	Somnolence (PT)
Loss of appetite	Decreased appetite (PT)
Fever	Pyrexia (PT)
Irritability	Irritability (PT)
Rash (all types combined)	Rashes, eruptions and exanthems NEC (HLT)

18.1.1.1. eCOA Compliance

Overall electronic diary (eCOA) compliance (across all eCOAs and all participants) for the study is calculated as:

$$\frac{\text{Total number of complete eCOAs}}{(\text{Expected number of complete eCOAs per participant} \times \text{Total number of participants})}$$

Where the expected number of complete eCOAs per participant is defined as 43, the number of days in which the eCOA is expected to be completed. This definition will also apply to participants who discontinue the study early.

An eCOA is considered complete if there is no missing data within the assessment. Solicited

Document: \\quintiles.net\enterprise\Apps\sasdata\SASb\SAS\GlaxoSmithKline\VNS\217212\VNS 20-006\Biostatistics\Documentation\SAP\ GSK_217212\VNS 20-006)_ZZA47662_SAP_Final_v7_24Jun2024.docx

Author: PPD Version Number: 7.0
 Version Date: 24Jun2024

Template No.: CS_TP_BS016 Revision 6

Reference: CS_WI_BS005

Effective Date: 02Dec2019

event data reported by the investigator will not contribute to eCOA compliance.

A participant is considered to be compliant with their eCOA if at least 80% of their eCOA are complete, i.e, a participant is compliant if they meet the following criteria:

$$\frac{\text{Total number of complete eCOAs}}{\text{Expected number of complete eCOAs}} \times 100 \geq 80\%$$

The overall compliance, and the number of participants who are 0 - <50% compliant, 50 - <80% compliant and $\geq 80\%$ compliant with eCOA assessments will be summarized for the Final Analysis.

